9.2 Operational definitions for s(AE)s or s(AR)

Known side effects of omega-3 fatty acids as listed in the section 4.8 of the Summary of Product Characteristics (https://www.medicines.org.uk/emc/product/1706) will be documented in the CRFs but will not be classed as s(AE) or s(AR) and will not be reported to the sponsor. All other side-effects will be reported.

Reference safety information: information on the safety of omega-3 fatty acids is obtained from the Summary of the Product characteristic (https://www.medicines.org.uk/emc/product/1706). All other s(AE)and s(AR) will be reported to the sponsor according to their SOPs.

Similarly, treatment which was elective or pre-planned, for a pre-existing condition not associated with any deterioration in condition, e.g. pre-planned hip replacement operation which does not lead to further complications, any admission to hospital or other institution for general care where there was no deterioration in condition, and treatment on an emergency, outpatient basis for an event **not** fulfilling any of the definitions of serious as given above and not resulting in hospital admission will not be classed as s(AE) or s(AR).

CONFIDENTIAL

Page 48 of 77

IRAS: 240464

Eudra CT number 2018-000963-99

Routinely breaking the blind in double blind trials could compromise the integrity of the trial. Breaking the blind will only take place where information about the participant's trial treatment is clearly necessary for the appropriate medical management of the participant. In all cases the Investigator would evaluate the causality and expectedness of SAEs as though the participant was receiving the active medication.

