6. ELIGIBILITY CRITERIA

Inclusion criteria

- (a) GP/physician diagnosed gout
- (b) Meets the American College of Rheumatology (ACR)/European League against Rheumatism
- (EULAR) classification criteria for gout
- (c) Willing to commence or increase dose of urate lowering treatment
- (d) Serum uric acid \geq 360 µmol/L at the screening visit
- (e) Age \geq 18 years at the screening visit
- (f) Able to give informed consent
- (g) No change in the average weekly dose of analgesics for at least 4 weeks prior to screening visit
- (h) Be able to adhere to the study visit schedule and other protocol requirements
- (i) Subjects able to communicate well with the investigator or designee, to understand and comply with

the requirements of the study and to understand and sign the written informed consent

(j) At least one gout flare in the previous 12 months

Exclusion criteria

a) Other defined inflammatory arthritis e.g. reactive arthritis, rheumatoid arthritis, psoriatic arthritis,

seronegative spondyloarthropathy, Lyme's disease, or plaque psoriasis

b) Other autoimmune inflammatory conditions like moderate/severe asthma or inflammatory bowel

disease requiring corticosteroids or immune suppressing treatments

c) Active solid organ cancer

CONFIDENTIAL

Page 32 of 77

IRAS: 240464

Eudra CT number 2018-000963-99

d) Dementia

e) Serious co-morbidities preventing prescription of treatment

f) On regular daily NSAIDs, or prednisolone, or colchicine and unable to discontinue them

g) On long-term anticoagulation: Because of the mild increase in bleeding time with 4 gm/day omega-3

fatty acids, there is a potential interaction with warfarin and an increased possibility of haemorrhage in

patients at high risk because of severe trauma, surgery, etc. Patients receiving anticoagulant therapy will

therefore be excluded.

h) Oral, intra-muscular, intra-arterial, or intra-venous corticosteroids during the last 1 month

i) Known allergy or hypersensitivity to omega-3 fatty acids, fish, gelatine, olive oil, and soya

j) Pregnant or planning to become pregnant during treatment period,

k) Breastfeeding or planning to breastfeed during treatment period,

I) Use of any investigational (unlicensed) drug within 3 month prior to screening or within 5 half-lives of the investigational agent, whichever is longer

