(SUSAR)	• in the case of a product with a marketing authorisation, in the summary of product characteristics (SmPC) for that product							
Expected Serious	Nil							
Adverse								
Events/Reactions								

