9.3 Recording and reporting of SAEs AND SUSARs

The period of time over which AEs, ARs, SAEs, SARs and SUSARs must be recorded and reported is:

- For SAEs consent
- For ARs / SARs and SUSARs from 1st IMP dose.

As omega-3 fatty acid capsules take 28 days to have an anti-inflammatory effect, any SAEs will be monitored for 28 days after last treatment dose. If the CI becomes aware of any SARs or SUSARs after the active monitoring period end, he will still inform the sponsor.

In all cases SAEs and SARs will be reported to the Sponsor, unless they are known side effects of omega-3 fatty acids.

All **SAEs** occurring from the time of **written informed consent** until 28 days post cessation of trial treatment must be recorded on the appropriate Form and faxed to the Sponsor **within 24 hours** of the research staff becoming aware of the event. Once all resulting queries have been resolved, the Sponsor will request the original form should also be posted to the Sponsor and a copy to be retained on site.

For each **SAEs** the following information will be collected:

- full details in medical terms and case description
- event duration (start and end dates, if applicable)
- action taken

CONFIDENTIAL

Page **49** of **77**

IRAS: 240464

Eudra CT number 2018-000963-99

- outcome
- seriousness criteria
- causality (i.e. relatedness to trial drug / investigation), in the opinion of the investigator
- whether the event would be considered expected or unexpected.

Any change of condition or other follow-up information should be faxed to the Sponsor as soon as it is available or at least within 24 hours of the information becoming available. Events will be followed up until the event has resolved or a final outcome has been reached.

All SAEs assigned by the CI or delegate as both suspected to be related to IMP-treatment and unexpected will be classified as SUSARs and will be subject to expedited reporting to the Medicines and Healthcare Products Regulatory Agency (MHRA). The Sponsor will inform the MHRA, the REC and the Sponsor of SUSARs within the required expedited reporting timescales.

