9.4 Responsibilities

Principal Investigator (PI):

Checking for AEs and ARs when participants attend for treatment/follow-up.

- 1. Clinical oversight of the safety of patients participating in the trial, including an ongoing review of the risk / benefit.
- Using medical judgement in assigning seriousness, causality and expectedness [in Phase III and late Phase II CTIMPs] using the Reference Safety Information approved for the trial.
- Using medical judgement in assigning seriousness and causality and providing an opinion on expectedness [in Phase I and early Phase II CTIMPs] using the Reference Safety Information approved for the trial.

CONFIDENTIAL

Page 51 of 77

IRAS: 240464

Eudra CT number 2018-000963-99

- 4. Ensuring that all SAEs and SARs (including SUSARs) are recorded and reported to the Sponsor (with the exceptions as outlined earlier), within 24 hours of becoming aware of the event and provide further follow-up information as soon as available. Ensuring that SAEs and SARs (including SUSARs) are chased with Sponsor if a record of receipt is not received within 2 working days of initial reporting.
- 5. Ensuring that AEs and ARs are recorded and reported to the Sponsor in line with the requirements of the protocol.
- 6. Immediate review of all SUSARs.
- 7. Review of specific SAEs and SARs in accordance with the trial risk assessment and protocol as detailed in the Trial Monitoring Plan.
- Assigning Medical Dictionary for Regulatory Activities (MedDRA) or Body System coding to all SAEs and SARs.
- Preparing the clinical sections and final sign off of the Development Safety Update Report (DSUR).

Sponsor:

- Central data collection and verification of AEs, ARs, SAEs, SARs and SUSARs according to the trial protocol.
- 2. Reporting safety information to the CI, delegate or independent clinical reviewer for the ongoing assessment of the risk / benefit according to the Trial Monitoring Plan.
- Reporting safety information to the Trial Steering Committee (TSC) according to the Trial Monitoring Plan.
- Expedited reporting of SUSARs to the Competent Authority (MHRA in UK) and REC within required timelines.
- 5. Notifying Investigators of SUSARs that occur within the trial.

CONFIDENTIAL

Page 52 of 77

IRAS: 240464

Eudra CT number 2018-000963-99

Page **53** of **77**

- The unblinding of a SAE for the purpose of expedited SUSAR reporting [For double blind trials only].

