10.6 Interim analysis and criteria for the premature termination of the trial

As the main purpose of this study is to determine the metrics of an adequately powered definitive trial we will not perform any interim analysis. This is also given the fact that omega-3 fatty acids are safe, low-risk, and do not carry risk of serious adverse events.

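### Sections 9.2 and 9.3 exempt SmPC-listed side effects from SAE status and sponsor reporting however serious they are, against the protocol's own definitions and its 24-hour rule

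*Protocol*

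**What the plan says.** Section 9.2 defines the exempt group as "Known side effects of omega-3 fatty acids as listed in the section 4.8 of the Summary of Product Characteristics". These effects "will be documented in the CRFs but will not be classed as s(AE) or s(AR) and will not be reported to the sponsor". All other side effects are reported.

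Section 9.3 carries the exemption over to serious events: "In all cases SAEs and SARs will be reported to the Sponsor, unless they are known side effects of omega-3 fatty acids". The investigator's duties in 9.4 refer back to these exceptions.

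Other parts of section 9 point the other way:

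- The 9.1 definition of an SAE covers every untoward occurrence that meets a seriousness criterion, including hospital admission and death. It makes no exception for listed effects.
- The 9.1 row for expected serious adverse events and reactions reads Nil.
- The paragraph of 9.3 that directly follows the exemption says that all SAEs from consent "until 28 days post cessation of trial treatment must be recorded on the appropriate Form and faxed to the Sponsor" within 24 hours. The SAE report must state whether the event was expected.
- Section 9.4 gives the sponsor "Central data collection and verification of AEs, ARs, SAEs, SARs and SUSARs according to the trial protocol".
- Section 9.5 limits the reporting of deaths to those judged to be caused by the IMP.

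**The concern.** Listing in the SmPC should decide whether a serious reaction is expected, and hence whether it is a SUSAR. Here it decides whether the event is an SAE at all. The exemption looks at the type of event and never at its outcome, so a listed effect that puts a participant in hospital is treated like a mild one.

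At stake is the flow of safety information. Under 9.4 the sponsor passes safety information to the Trial Steering Committee and prepares the standard tables for the annual safety report. The steering committee carries the decision on stopping for safety, and no DMC is convened. An event that is never sent to the sponsor is missing from that route. Site staff dealing with such an event would also find opposite instructions in adjacent paragraphs of 9.3.

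**Working it through.** The protocol states no figure on this point, so the check sets its provisions side by side. Take one case: a participant is admitted to hospital with a side effect that is listed in SmPC 4.8.

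| Provision | Status of the event | Sent to the sponsor? |
|---|---|---|
| 9.1, SAE definition | SAE (hospital admission) | follows from SAE status |
| 9.1, expected serious events: Nil | Serious and not expected; a SUSAR if judged related | Yes |
| 9.2, listed effects | Neither s(AE) nor s(AR) | No |
| 9.3, sentence with the exception | SAE or SAR, but a known side effect | No |
| 9.3, next paragraph | SAE | Yes, within 24 hours, expectedness stated |

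**Step 1: does the exemption reach serious events?** The notation s(AE) in 9.2 could mean AEs and SAEs, or SAEs only. Serious events are exempt on either reading, and 9.3 removes any doubt by naming SAEs and SARs.

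**Step 2: does it affect SUSARs?** Section 9.3 draws SUSARs from SAEs that are related and unexpected. Section 9.1 defines a SUSAR as a serious adverse reaction whose nature and severity do not fit the SmPC. A listed effect in a more severe form than the SmPC describes could therefore be a SUSAR. Read literally, 9.2 removes it from the SAE and SAR classes before that question is asked.

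**Step 3: what is still recorded?** The effects are documented in the CRF. Appendix 2 has side effects assessed at every visit from week 5 to week 28 and at the final safety call. The protocol does not say that an exempt effect is recorded with the seriousness criterion, causality and expectedness that 9.3 asks for on SAEs.

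**Step 4: would a comparison between arms be distorted?** Only under conditions. Let *l* be the risk of a listed effect in an arm and *u* the risk of any other event, equal in both arms and independent of *l*. Then

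risk of any event = 1 − (1 − *l*)(1 − *u*)

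difference between arms = (1 − *u*)(*l*_active − *l*_placebo)

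All risks below are assumptions, since the protocol gives none. *u* runs from 5% to 20%.

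| *l* active vs placebo | All recorded events | Classed events only |
|---|---|---|
| 20% vs 10% | 8 to 9.5 points | 0 |
| 30% vs 10% | 16 to 19 points | 0 |
| 40% vs 10% | 24 to 28.5 points | 0 |
| 20% vs 20% | 0 | 0 |

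For the second row, 0.80 × 0.20 = 0.16 and 0.95 × 0.20 = 0.19. An excess disappears only if omega-3 raises listed effects and the table counts classed events only.

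**The case against.** The strongest defence is that the text can be read as a general rule with a stated exception. The exception stands immediately before the 24-hour rule and 9.4 refers back to it. Nil may mean only that no serious listed effect was foreseen, so that the exemption was written with minor effects in mind. An event more severe than the SmPC describes is arguably not a known effect as listed, and 9.3 separately requires SUSARs within 24 hours. These readings are open, but none is written down. The exception names SAEs and SARs, so it is not confined to minor effects.

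A reader might infer more than the protocol supports:

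- **That AE and SAE counts by arm are biased toward no difference.** The protocol specifies no such count. Section 10.3.3 gives only means and percentages for secondary outcomes. The one safety-type outcome, withdrawal because of side effects, does not depend on AE or SAE class. A statistical analysis plan, which is not shown, may use the CRF records.
- **That the events are lost.** They are kept from the sponsor but recorded in the CRF. The investigator keeps clinical oversight and the steering committee reviews safety data periodically. The supportable harm is incomplete information.
- **That bleeding events in particular are exempt.** Exclusion (g) mentions haemorrhage as the reason for excluding anticoagulated patients. It does not show that haemorrhage is listed in SmPC 4.8. The statement in 10.6 that omega-3 fatty acids "do not carry risk of serious adverse events" supports the absence of an interim analysis and is a separate matter.

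**Conclusion.** The rule is wrong as written and should be corrected. Sections 9.2 and 9.3 exempt SmPC-listed effects from SAE and SAR status and from sponsor reporting at every level of seriousness. That cannot be squared with the SAE definition, the entry Nil, or the all-SAE rule. The conclusion rests on the protocol text alone. It does not require SmPC 4.8 to list any reaction as serious, because any listed effect becomes serious if it leads to admission.

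The scope of the exemption is every listed effect, but the number of serious events that it would withhold among the planned 60 participants is unknown and may be zero. Distortion of a comparison between arms is a conditional risk and is not a property of the stated analysis. A statistical analysis plan could settle which events are tabulated. It could not repair expedited reporting, which the protocol governs.

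**What to change.** Reconcile 9.1, 9.2 and 9.3 along these lines:

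1. SmPC-listed effects are recorded in both arms and classified by the 9.1 definitions.
2. Any event that meets a seriousness criterion is an SAE or SAR and goes to the sponsor within 24 hours, listed or not.
3. SmPC listing affects only expectedness, and so SUSAR status. The Nil entry in 9.1 is worded to agree with this.
4. Only non-serious listed effects are exempt from individual reports to the sponsor. The exception in 9.3 and the reference to it in 9.4 are limited accordingly.
5. Section 9.5 is brought into line. A death meets the first seriousness criterion in 9.1, yet 9.5 reports only deaths judged to be caused by the IMP.

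State also that any safety summary by arm uses all CRF-recorded events, listed or not.

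The cost is a change of protocol wording and possibly a few extra SAE forms. Listed effects are already recorded in the CRFs, so no new visit or assessment is needed.

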9.3 Recording and reporting of SAEs AND SUSARs

The period of time over which AEs, ARs, SAEs, SARs and SUSARs must be recorded and reported is:

- For SAEs consent
- For ARs / SARs and SUSARs from 1st IMP dose.

As omega-3 fatty acid capsules take 28 days to have an anti-inflammatory effect, any SAEs will be monitored for 28 days after last treatment dose. If the CI becomes aware of any SARs or SUSARs after the active monitoring period end, he will still inform the sponsor.

In all cases SAEs and SARs will be reported to the Sponsor, unless they are known side effects of omega-3 fatty acids.

All **SAEs** occurring from the time of **written informed consent** until 28 days post cessation of trial treatment must be recorded on the appropriate Form and faxed to the Sponsor **within 24 hours** of the research staff becoming aware of the event. Once all resulting queries have been resolved, the Sponsor will request the original form should also be posted to the Sponsor and a copy to be retained on site.

For each **SAEs** the following information will be collected:

- full details in medical terms and case description
- event duration (start and end dates, if applicable)
- action taken

CONFIDENTIAL

Page **49** of **77**

IRAS: 240464

Eudra CT number 2018-000963-99

- outcome
- seriousness criteria
- causality (i.e. relatedness to trial drug / investigation), in the opinion of the investigator
- whether the event would be considered expected or unexpected.

Any change of condition or other follow-up information should be faxed to the Sponsor as soon as it is available or at least within 24 hours of the information becoming available. Events will be followed up until the event has resolved or a final outcome has been reached.

All SAEs assigned by the CI or delegate as both suspected to be related to IMP-treatment and unexpected will be classified as SUSARs and will be subject to expedited reporting to the Medicines and Healthcare Products Regulatory Agency (MHRA). The Sponsor will inform the MHRA, the REC and the Sponsor of SUSARs within the required expedited reporting timescales.

All **SUSARs** occurring from the time of **start of trial treatment** until 28 days post cessation of trial treatment must be recorded on the relevant form and faxed to the Sponsor **within 24 hours** of the research staff becoming aware of the event. Once all resulting queries have been resolved, the Sponsor will request the original form. The original form should be posted to the Sponsor and a copy to be retained on site.

For each SUSARs the following information will be collected:

- full details in medical terms and case description
- event duration (start and end dates, if applicable)
- action taken
- outcome

CONFIDENTIAL

Page **50** of **77**

IRAS: 240464

Eudra CT number 2018-000963-99

- seriousness criteria
- causality (i.e. relatedness to trial drug / investigation), in the opinion of the investigator
- whether the event would be considered expected or unexpected.

Any change of condition or other follow-up information should be faxed to the Sponsor as soon as it is available or at least within 24 hours of the information becoming available. Events will be followed up until the event has resolved or a final outcome has been reached.

Sponsor Contact Details for SAEs:

- I. Email ([contact])
- II. Hand delivered not mailed ([name])
- III. [contact]) if written report not immediately possible

9.4 Responsibilities

Principal Investigator (PI):

Checking for AEs and ARs when participants attend for treatment/follow-up.

- 1. Clinical oversight of the safety of patients participating in the trial, including an ongoing review of the risk / benefit.
- Using medical judgement in assigning seriousness, causality and expectedness [in Phase III and late Phase II CTIMPs] using the Reference Safety Information approved for the trial.
- Using medical judgement in assigning seriousness and causality and providing an opinion on expectedness [in Phase I and early Phase II CTIMPs] using the Reference Safety Information approved for the trial.

CONFIDENTIAL

Page 51 of 77

IRAS: 240464

Eudra CT number 2018-000963-99

- 4. Ensuring that all SAEs and SARs (including SUSARs) are recorded and reported to the Sponsor (with the exceptions as outlined earlier), within 24 hours of becoming aware of the event and provide further follow-up information as soon as available. Ensuring that SAEs and SARs (including SUSARs) are chased with Sponsor if a record of receipt is not received within 2 working days of initial reporting.
- 5. Ensuring that AEs and ARs are recorded and reported to the Sponsor in line with the requirements of the protocol.
- 6. Immediate review of all SUSARs.
- 7. Review of specific SAEs and SARs in accordance with the trial risk assessment and protocol as detailed in the Trial Monitoring Plan.
- Assigning Medical Dictionary for Regulatory Activities (MedDRA) or Body System coding to all SAEs and SARs.
- Preparing the clinical sections and final sign off of the Development Safety Update Report (DSUR).

Sponsor:

- Central data collection and verification of AEs, ARs, SAEs, SARs and SUSARs according to the trial protocol.
- 2. Reporting safety information to the CI, delegate or independent clinical reviewer for the ongoing assessment of the risk / benefit according to the Trial Monitoring Plan.
- Reporting safety information to the Trial Steering Committee (TSC) according to the Trial Monitoring Plan.
- Expedited reporting of SUSARs to the Competent Authority (MHRA in UK) and REC within required timelines.
- 5. Notifying Investigators of SUSARs that occur within the trial.

CONFIDENTIAL

Page 52 of 77

IRAS: 240464

Eudra CT number 2018-000963-99

Page **53** of **77**

- The unblinding of a SAE for the purpose of expedited SUSAR reporting [For double blind trials only].
- Checking for (annually) and notifying PIs of updates to the Reference Safety Information for the trial.
- 8. Preparing standard tables and other relevant information for the DSUR in collaboration with the CI and ensuring timely submission to the MHRA and REC.

Trial Steering Committee (TSC):

In accordance with the Trial Terms of Reference for the TSC, periodically reviewing safety data and liaising with the sponsor regarding safety issues.

Data Monitoring Committee (DMC):

Given the feasibility nature of this study, and low-risk profile of omega-3 fatty acids we will not convene a DMC. Additionally, the safety profile of omega-3 fatty acids is well known and this medicine has been licenced for several years for indications other than gout.

